Standardized Patient Encounters to Improve Counseling for Pre-Exposure Prophylaxis (PrEP) for HIV Prevention to Adolescent Girls and Young Women (AGYW) in Kenya

Grant Number: R01 HD094630

Principal Investigators: [name], MPH, RN and [name], PhD

Version Number: 1.3

May 16, 2019

SUMMARY

Background: The incidence of HIV in adolescent girls and young women (AGYW) continues to rise despite promising innovation in female-controlled HIV prevention strategies. In 2016, 34,000 women ages 15+ were infected with HIV in Kenya. Pre-exposure prophylaxis (PrEP) has been shown to reduce the risk of HIV acquisition through sexual intercourse by 92% among sero-discordant partners. While PrEP is a highly efficacious intervention, its real-world effectiveness at scale is threatened by low adherence. Improving medication adherence through improved health counseling at the first clinical consultation is necessary. Standardized patient actors (SPs) are an effective tool for health providers to improve communication and counseling skills. Evaluating the effectiveness of SP education for health care workers (HCWs) delivering PrEP to AGYW can identify new training approaches to facilitate improved communication and PrEP delivery for AGYW seeking PrEP services in Kenya.

Goal: To facilitate AGYW uptake of and adherence to PrEP through a clinical training program using SPs to improve HCW communication skills and delivery of PrEP counseling services to AGYW at risk for HIV.

Aims:

1. To assess quality of PrEP counseling and adherence to National AIDS and STI Control Programme (NASCOP) guidelines among HCWs delivering PrEP to AGYW in Kenya.
2. To implement and evaluate the effectiveness of an SP training intervention designed to improve HCW counseling and communication skills, and adherence to national guidelines, in delivery of PrEP to AGYW in Kenya

Methods: During the first phase (Aim 1) we will conduct a cross-sectional baseline assessment of PrEP counseling practices using unannounced SP actors as evaluators at 24 facilities in Western Kenya. We will then randomly assign 12 facilities to an SP training intervention and 12 facilities to a control arm where they will continue standard of care (Aim 2). We will evaluate outcomes of the training program through a parallel cluster-randomized trial, repeating the cross-sectional unannounced SP assessment.

Population: HCWs who provide HIV care and treatment and/or PrEP services in Western Kenya.

Outcomes: The primary outcome will be quality of the PrEP counseling session, defined as adherence to NASCOP guidelines of PrEP counseling/delivery and use of non-judgmental interpersonal skills, and measured as a score on a SP checklist after unannounced visits. The secondary outcome will be HCWs communication quality, including clarity of information, non-judgment, listening without interruption, encouraging questions, empathetic statements, and showing interest in the patient's concerns.

Timeframe: January 2019 to August 2022

TABLE OF CONTENTS

Title page	1
Summary	2
Table of contents	3
List of abbreviations	4
Key roles and contacts	5-6
Collaborations	6
Background and Literature Review	7-8
Rationale	9
Aims	9
Outcome measures	9
Methods	
Study design	10
Population and setting	10
Eligibility criteria	10
Sampling and sample size	10
Randomization	10
Recruitment	10-11
Study procedures	11
Data collection	11-13
Statistical analysis	11
Sample size and power	11-12
Data management	14-15
Dissemination and Impact	15
Ethic/Protection of study participants	
Human subjects monitoring plan	15
Informed consent process	15-16
Participant withdrawal	16
Participant confidentiality	16
Risks and benefits	16-17
Safety management	17
Study schedule	18
Budget	19
References	20-21

LIST OF ABBREVIATIONS

AGYW	Adolescent girls and young women
ARV	Antiretroviral drugs
ERC	Ethics Review Committee
GoK	Government of Kenya
HCWs	Health care workers
HIV	Human immunodeficiency virus
IDI	In-depth interviews
IRB	Institutional Review Board
KNH	Kenyatta National Hospital
MOH	Ministry of Health
NASCOP	National AIDS and STI Control Programme
PrEP	Pre-exposure prophylaxis
RCT	Randomized control trials
SPs	Standardized Patient Actors
STI	Sexually transmitted infection
UON	University of Nairobi
UW	University of Washington
WHO	World Health Organization

KEY ROLES AND CONTACTS

National AIDS & STI Control Programme (NASCOP)
Afya Annex
Kenyatta National Hospital Grounds
[name]
Nairobi, Kenya

Funding **Funding type:** Grant
Funding agency: The Eunice Kennedy Shriver National Institute of Child Health and Human Development (NICHD), National Institutes of Health (NIH)
Principal Investigator on Proposal: [name], [name]
Proposal Identification Number: 1 R01 HD094630-01
Title: PrEP Adherence Among AGYW: A Multidimensional Evaluation
Dates: 07/01/17-6/30/22

BACKGROUND AND LITERATURE REVIEW

1a. Background Information

Adolescent girls and young women experience a disproportionate risk of HIV infection: Adolescent girls and young women (AGYW) in Southern and Eastern Africa are at high risk of HIV acquisition. In 2015, an estimated 390,000 new HIV infections occurred in AGYW ages 15-24, globally, and AGYW have a 9-fold increase in HIV prevalence compared with males of the same age (2). Recent HIV prevention trials also show higher HIV incidence in AGYW cohorts than in cohorts of women in sero-discordant partnerships (Figure 1) (3-7). In these trials, the incidence of HIV among AGYW ranged from 5 to 9.1 HIV infections/100 person-years (3-7). The 2016 United Nations Global Assembly Fast Track goals aim to decrease the annual number of new HIV infections among 15 to 24-year-old women to 100,000. This will require a 74% reduction in the current annual number of AGYW infected with HIV (8).

PrEP is an effective tool to decrease HIV incidence in young women:

The United Nations recommends a multifaceted approach that addresses structural determinants and gender inequity while leveraging powerful new biomedical tools for HIV prevention (9-12). Biomedical interventions, including expansion of antiretroviral treatment (ART) combined with pre-exposure prophylaxis (PrEP), offer alternatives to complement structural approaches to rapidly decrease HIV incidence in AGYW. PrEP, a once a day, oral ARV medication consisting of tenofovir (TDF) and emtricitabine (FTC), also known under the brand name, Truvada, has been shown to effectively prevent HIV transmission among sero-discordant partners (13, 14). In the Partners PrEP study among HIV uninfected women in sero-discordant partnerships, TDF-PrEP had 71% efficacy and TDF/FTC-PrEP had 66% efficacy; (3, 14, 15). High HIV incidence in AGYW necessitates action, and PrEP implementation is a practical intervention.

Although PrEP is effective, adherence has been poor among AGYW participating in PrEP RCTs: Sub-analyses of women in the Partners randomized control trial (RCT), showed that even among women with HIV risk factors such as high partner viral load count, unprotected sex, or diagnosis of a sexually transmitted infection (STI), PrEP retained efficacy (16). However, to maximize PrEP effectiveness as an HIV prevention tool, high adherence to regimens is required. Momentum to scale-up PrEP was suppressed when two large RCTs of PrEP among young women, VOICE and FEMPrEP, failed to show PrEP efficacy, due to low retention and low PrEP adherence (5, 6, 17, 18). A more recent meta-analysis of 5 PrEP studies in women estimated that PrEP would have had a protective effect, with a RR of 0.69 with PrEP if women had at least 75% adherence (19). As countries like Kenya [49] expand the availability and use of PrEP, it is imperative that efforts to scale-up PrEP in AGYW also focus on adherence.

Health system interactions may influence PrEP uptake and adherence among AGYW: PrEP studies often involve project-dedicated staff who commit to optimizing interactions with clients, providing in-depth and thoughtful HIV prevention counseling and PrEP messaging. Initiatives for PrEP use in AGYW involve programmatic expansion into the public health sector and require an understanding of user experiences and motivation of AGYW as well as optimization of health system interactions within an already over-extended system (Figure 2). Health systems interactions, led by HCWs lacking training, resources, skills, or empathy, have been shown to decrease AGYW uptake of sexual and reproductive health services (20-22). Among AGYW, stigma, HCW bias, and HCW discrimination have been reported to be common and major barriers to uptake of health care and HIV services, (23-25). These barriers may influence AGYW's attempt to seek and continue preventative services, like PrEP.

[figure not shown]

Figure 1. New HIV infections by sex, sub-Saharan Africa, 2015 (1)

[figure not shown]

Figure 2. User experience and the health system interactions influence PrEP adherence

Standardized patient actors can accurately assess health service quality: Standardized patients (SPs) are actors who have been trained to portray patients in scripted, medically-themed scenarios for student and HCW evaluation and education. This style of training has been used since the 1960s in clinical and medical education (12). SPs have been used to develop and improve skills related to patient-centered communication: empathy, communication skills, and counseling for HCWs. As an evaluation tool, SPs are considered the gold-standard in measuring care quality (12) and can accurately assess the competencies of a provider in a variety of clinical and teaching settings. (14-17).

SP training programs can improve quality of care in low and middle-income countries (LMIC): In LMIC settings, SPs have been used to evaluate how services are delivered in practice. In a systematic review of 31 LMIC pharmacy studies, SPs helped identify whether providers were or were not adhering to prescription and diagnosis treatment guidelines (26). This review found that SPs were useful in describing counseling practices of pharmacists, however, few studies used SPs to provide feedback to HCWs. Global TB and STI program evaluations used SPs to demonstrate non-standard practices by clinical providers (27, 28). Additionally, SPs were effective in training nurses and midwives in obstetric care to improve provider self-efficacy in emergent obstetric situations (29).

A training intervention using SPs may improve the effectiveness of PrEP scale up for AGYW: Medical care involves transfer of information and skills in communication, cultural competence, and empathy. Use of SPs offers a pragmatic and effective way to improve HCW skills to facilitate PrEP counseling and delivery to AGYW. Ensuring AGYW take PrEP regularly decreases risk of acquiring HIV, interrupting the cycle of HIV transmission. Through this interruption, PrEP can ultimately reduce new HIV infections, bringing the world one step closer towards reaching the UNAIDS goal of 90-90-90 by 2020 (30).

1b. Rationale

High HIV incidence in AGYW demands an urgent response and PrEP implementation is a reasonable approach. As countries like South Africa (31) and Kenya (32) expand PrEP it is paramount that efforts to scale PrEP in AGYW do so in a manner that ensures adherence – otherwise these efforts are futile.

Offering PrEP to AGYW requires several challenging steps for busy HCWs, including incorporating discussion of HIV risk, providing information about PrEP, and encouraging PrEP adherence. Training health care workers for new programs typically incorporates didactic sessions but few practical tips on how to optimize interactions with clients. For clinicians working with adolescents, adolescent-friendly communication skills need to be trained. Medical care involves transfer of information and soft skills in communication, cultural competence, and empathy. Use of SPs, the gold standard for clinical training and assessment in high-resource settings, are a pragmatic and potentially effective way to improve HCW skills to facilitate PrEP delivery to AGYW. Clinical providers want to be 'youth friendly' but lack competence in this area, and often feel particularly unprepared for discussion of sexual risk with adolescents.

SPs have been widely used for medical education since the 1960s, both for training and licensing. In 2011, 90% of AAMC surveyed-US medical schools used SPs in medical training (33). A review of SP studies in 2016 found that 24 of 33 SP programs were effective in increasing clinical competence (34). Experiential learning leads to enhanced competence in motivational interviewing; SPs (high school students) have been useful in US settings to provide medical students experiential learning in communication with adolescents (35, 36). SPs have been shown to improve cultural competence in US providers (37). SPs can work with HCWs by acting out scenarios to help HCWs practice their communication strategies and be evaluated and provided with feedback regarding how to improve their abilities in counseling, information, and empathy.

Providing SPs to HCW to guide the process of navigating challenging scenarios, like working with AGYW to use and adhere to PrEP, can provide HCWs competency and confidence that makes their interactions with AGYW easier and more effective in practice.

There is substantial evidence that HCW interactions with SPs can improve service delivery and patient outcomes, though few data are available within the context of HIV prevention services among AGYW in African settings. Evaluating the effectiveness of SP education for HCWs within the context of PrEP use among AGYW populations will inform new training approaches to improve PrEP delivery practices and communication with AGYW in clinical settings. This study will address the gaps in delivering quality of PrEP services to AGYW through the following specific aims:

2. SPECIFIC AIMS

Aim 1: To assess quality of PrEP counseling and adherence to National AIDS and STI Control Programme (NASCOP) guidelines among HCWs delivering PrEP to AGYW in Kenya.

Aim 2: To implement and evaluate the effectiveness of an SP training intervention designed to improve HCW counseling and communication skills, and adherence to national guidelines, in delivery of PrEP to AGYW in Kenya.

3. STUDY OUTCOMES

The primary outcome will be quality of PrEP counseling, summarized by an SP checklist score at unannounced clinic visits that will assess communication (e.g. listening without interruption, encouraged questions) and adherence to national guidelines on PrEP counseling and delivery (e.g. risk assessment, counseling on key messages, correct medication recommended). The secondary outcome will be overall quality of provider communication skills with AGYW seeking PrEP services, measured by a score from SPs during the provider training intervention incorporating key domains including: ability to collect information, counseling and delivering information, rapport, and personal manner. Communications measures are adapted from the Kalamazoo Consensus Statement (38) and other published tools (39-41).

4. STUDY DESIGN

During the first phase (Aim 1) we will conduct a cross-sectional baseline assessment of PrEP counseling practices using unannounced SP actors as evaluators. SP actors are trained professional actors recruited from a Kenyan casting agency. They will be paid study staff, managed by our Study Coordinator. Before the study, actors will be trained in the SP methodology based on the study protocol. All SP actors will sign a confidentiality agreement and complete protection of human participants training before any contact with participants. Based on this assessment, we will develop and implement a clinical training program utilizing SP actors to improve adherence to national guidelines and communication skills. Finally, we will evaluate the training program through a parallel cluster-randomized trial of the SP training using repeat unannounced SP encounters at 24 health facilities purposively selected from all facilities in Western Kenya offering PrEP (Aim 2).

5. STUDY ENROLLMENT

5a. Population and Setting

The study will be implemented in 24 large public health facilities that provide PrEP care and counseling services to AGYW in Kisumu and other counties in Western Kenya. The facilities were purposively selected by the study team from among all facilities offering PrEP (37) based on factors such as size, location, and receptiveness of the facility to host research. The purposively selected study sites are: Chiga, Chulaimbo, Manywanda, Muhoroni, Nyalenda, Awasi, Koru, Ahero, Rabour, Lumumba, KCH, Migosi, Nightingale, Airport, Maseno, Bar Korwa, Railway, Rata, Nyan'goma, Nyalunya, Nyangande, Sondu, Ober-Kamoth, and Ojolla. At each site, the study will include HCWs who provide HIV care and PrEP services for AGYW. Inclusion and exclusion criteria are shown in Table 1, below.

5b. Eligibility criteria

Health Facility: Eligible facilities will include public health facilities that offer PrEP services and counseling to AGYW located within Western Kenya. Facilities with ongoing PrEP interventions where study staff will be excluded.

HCW participants: Eligible HCWs will be 18 years or older, current employees of one of the 24 facilities in the study, provide PrEP services to AGYW, and be able to provide informed consent. In Kenya, HCWs who provide PrEP therapy and counseling are most commonly trained nurses. The nurses are specifically trained in delivering PrEP per NASCOP guidelines.

Table 1. Inclusion Criteria

Population	Selection	N	Inclusion Criteria	Exclusion Criteria
Health Facilities	Facilities in Western County providing PrEP services for AGYW	24	Located in a county in Western Kenya Currently offering PrEP services	Sites where PrEP services are staffed by study staff
HCWs at selected facilities	HCWs working in any of the selected health facility sites	Up to 240	Age 18 or over Able to provide consent Current employee of one of the 24 selected facilities Currently providing PrEP services	Study staff seconded to the site as part of a trial or intervention

5c. Randomization

Randomization will occur at the cluster level: 24 facilities will be purposively selected from a list of all facilities in Western Kenya with PrEP services. We will use stratified randomization, through which 12 facilities will be allocated to the intervention and 12 will be assigned standard of care according to facility size, to ensure balance by arm. A UW biostatistician will generate the randomization assignment for each clinic.

5d. Recruitment

We will obtain permission from the NASCOP and local county and district officials to include these facilities in our study. At each clinic, we will obtain permission from the appropriate facility leadership before recruitment and receive a list of all potential HCW participants. All HCWs who meet inclusion criteria from both control and intervention groups will be recruited to participate in the study. A member of the study team will be stationed at the facility and approach potential participants to learn more about the study and provide informed consent. Based on previous studies, we estimate 10 HCWs per site, totaling approximately 240 HCWs.

5e. Participant withdrawal and replacement

Study facilities and participants may withdraw at any time. Reasons for a facility to withdraw may include closure or major changes in PrEP policies or procedures that would prevent or substantially limit ability to conduct the study. HCW participants may withdraw due to discomfort with the training, relocation, or leave of absence. The study team will record the timing and reasons for withdrawal of clinics or participants. Potential replacement of study facilities or HCW participants will be conducted but will not be required if it is not feasible because of design and logistical challenges.

6. STUDY PROCEDURES

6a. Stakeholder engagement

After obtaining NASCOP and local county and district official permission to enroll clinical study sites, the study team will meet with clinic leadership and managers to receive an overview of the study flow and procedures, and informed consent processes for participation (Figure 3).

6b. Case script development and SP actor training

Qualitative themes from previously conducted AGYW IDIs and focus group discussions, national guidelines, and key informant experiences will inform development of standardized case scripts. We will train professional Kenyan actors matching the ethnicity and languages of the local area to role play AGYW PrEP scenarios for both the unannounced assessments and HCW training. All SP actors are hired study staff. SP actors will be selected by a Kenyan casting agency based on their ability as actresses and their age, ethnicity, and language characteristics which match AGYW visiting health facilities in Western Kenya. The SP actors will be trained in the SP methodology by an expert consultant hired onto this study for this purpose. The SP actors will be trained on the specific standardized case scripts by study staff who are familiar with scenarios of AGYW seeking PrEP in Western Kenya.

6c. Baseline health services evaluation

A health facility survey will be administered to the facility manager in each facility to obtain baseline site characteristics on staffing, guidelines, and PrEP services. Unannounced SP actors will present to all study sites as AGYW seeking PrEP or HIV health services for an estimated 2-3 encounters per clinic. During the clinic encounter, SPs will act out their scripted scenario with enrolled HCW. After the encounter, the study assistant will administer a post-consultation questionnaire with the SP and will also work with the health facility to remove the SP information from the clinic forms and registers. Results from the baseline assessment will inform the HCW training on PrEP service delivery.

6d. HCW SP Training on PrEP services

All HCW participants at intervention facilities will be invited to complete a 2-day training. The course will provide didactic sessions in communication skills, current PrEP guidelines, and counseling techniques, as well as role play sessions with the SPs. We aim to train all eligible HCWs at intervention facilities in small groups of 5-10. HCW-SP interactions will be video-recorded for training purposes. SPs will give verbal and written feedback on communication and counseling skills and will score HCWs using a standardized checklist. Facilitated group debriefings will take place at the end of each day, including review and discussion of selected videos. HCWs will complete a course evaluation and pre/post competency surveys. HCWs employed at the study facilities assigned to the control arm will not receive this training. They will perform their routine duties according to standard of care and will only take part in the unannounced SP assessments.

6e. Training evaluation

Once training is complete for all sites, unannounced SPs will repeat the assessment conducted during the baseline evaluation at all 24 intervention and control sites.

[figure not shown]

Figure 3. Study Schema

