7. DATA COLLECTION

Health facility survey: This anonymous survey will be administered to a health facility manager at baseline to capture facility characteristics (number of staff, patient demographics, services provided, etc.), including turnover of SP-trained HCWs, patient volume, and any relevant changes in HIV policies and procedures.

Unannounced SP checklist: A survey will be completed by each SP actor, following every clinical interaction with an HCW provider using electronic tablets. The surveys will be conducted at baseline and after the HCW training at all 24 sites. The tool will assess domains of counseling and communication skills, and adherence to national PrEP guidelines.

SP training checklist: Standardized SP checklists will be used to evaluate the HCW encounter with the SP actor. The SP will complete checklists based on individual scenarios to provide feedback for the HCW on their practice session and provide a score based on competencies met.

HCW surveys: HCW participants will complete surveys prior to and after the SP training to assess knowledge of and self-rated competency in provision of PrEP to AGYW, beliefs about AGYW and HIV, and basic demographic and work information.

HCW training evaluation surveys: Post-training surveys will be administered to HCW participants to obtain feedback on the quality, length, and relevance of the SP training.

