9. DATA MANAGEMENT

A dedicated data team will be responsible for the entry, management, and monitoring of study data, in accordance with standard operating procedures. The Nairobi data team will communicate frequently with the Seattle-based statistical team for reporting, data cleaning, study monitoring, and interim analyses. Study data will be uploaded to the secure study cloud server using REDCap. REDCap is a secure, web-based application designed to support data capture and management for research studies. The software provides 1) an intuitive interface for validated data entry; 2) automated export procedures for seamless data downloads; and 3) procedures for importing data from external sources.

9a. Data Capture and Storage Methods

Video-recordings: Videos from HCW participants in SP training who have consented to allow their videos to be used for further training purposes will be stored on a secure server for at least three years after completion of the study by the University of Washington.

Surveys and unannounced SP checklist: Health facility surveys and the unannounced SP checklist will be administered by study staff via electronic tablets using REDCap data collection software and uploaded daily during survey capture periods. Data will be transported via secure socket layer (SSL) and only accessible by authenticated users. Weekly reports will be generated to monitor study progress and troubleshoot problems. All computers, tablets, and individual study databases will be encrypted, and password protected.

SP training checklist: Data from the checklist will be shared with the HCW during the training session. The original paper copies of the checklist will be identified using a study ID number. They will be stored in a secured locked cabinet in a study office accessible only to study staff.

Data Custody and Retrieval: All data for this study will be under the custody of the Principal Investigators, Site PI, and authorized study staff. Data retrieval procedures will be similar for all types of data in this study. Authorized study staff members will download the datasets from the secure servers for routine quality checking and analyses. All downloaded data will be maintained on a secured, password-protected study computer. From these data sources, the analysts will create merged datasets for planned analyses.

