The primary outcome of the trial will be quality of PrEP counseling, summarized by an SP checklist score at unannounced clinic visits that will assess communication (e.g. listening without interruption, encouraged questions) and adherence to national guidelines on PrEP counseling and delivery (e.g. risk assessment, counseling on key messages, correct medication recommended). The secondary outcome, assessed in intervention arm will be change in interpersonal skills mean score percent between the first and last session. Communications and interpersonal skills measures are adapted from the Kalamazoo Consensus Statement (31) and other published tools (32-34)

SAMPLE SIZE CONSIDERATIONS

Primary trial outcome: Given a fixed number of clusters (24 facilities), we estimated the minimum number of SP encounters required to detect a 20 percentage-point difference in PrEP counselor competency score between intervention and control arms. Because it is uncertain what baseline PrEP competency will be, we estimated sample sizes to detect a 10-percentage point difference between the intervention and control arm varying the baseline competency percent, shown in Table 2. Under these assumptions, if PrEP competency is 61% in the control arm using baseline data and standard deviation of 17.7%, we would need an estimated 112 to 120 total SP encounters (4 to 6 per site). We will plan to conduct 6 visits per site (120 total), which assumes we only have 20 facilities, to ensure we have adequate power. Higher baseline competency would require a larger sample size to detect the same difference. The expected upper limit of SP encounters is 400.

Table 1. Sample sizes of SP encounters to detect a 10-percentage point difference in competency at 80% power, correlation coefficient (k) of 0.15, $\alpha=0.05$ and 24 facilities

Control group competency %	Intervention group competency %	Minimum cluster per arm required	SP encounters per cluster	Total SP encounters
0.61	0.71	14	4	112
0.61	0.71	11	5	110
0.61	0.71	10	6	120
0.61	0.71	8	7	112
0.61	0.71	8	8	128
0.61	0.71	7	9	126
0.61	0.71	6	10	120
0.61	0.71	6	11	132
0.61	0.71	6	12	144

STATISTICAL ANALYSES AND DESCRIPTION OF MAIN TABLES

Cluster RCT of PriYA-SP intervention

Question: Does the SP training intervention improve *quality* of provider delivery of PrEP services?

Overview: The primary analysis will evaluate effectiveness of the SP clinical training intervention on provider counseling skills and adherence to national guidelines

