5. APPENDICES

APPENDIX 1: DATA SOURCES

Data source	Description	Timing of data collection	Analysis purpose
Unannounced SP checklist	Standardized SP checklists to evaluate the HCW encounter with the SP actor at baseline and endline unannounced visits	Baseline and end of study	Primary outcome End of study scores will be compared between RCT arms; Baseline scores used as an adjustment variable
Facility Survey	Anonymous survey will be administered to a health facility manager at baseline to capture facility characteristics	Baseline	Assess adequacy of randomization; Provide data for potential adjustment of ITT analysis
HCW surveys	Pre/post surveys to assess knowledge of and self-rated competency in provision of PrEP to AGYW	Baseline and end of study	Assess change in knowledge/attitudes between baseline and end of study, all sites Compare end of study scores between trial arms
SP training checklist	Standardized SP checklists to evaluate quality of the simulated visit with HCWs in the intervention training	Immediately after each SP encounter among trial participants	Secondary outcome Change in mean competency % among intervention participants between the first and last session

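### The secondary outcome is an uncontrolled change scored by actors who also give the trainees feedback, and nothing stops the last session being scored by an actor who has already given that HCW feedback

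*Protocol*

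**What the plan says.** The SAP (Study Outcomes) defines the outcome: "The secondary outcome, assessed in intervention arm will be change in interpersonal skills mean score percent between the first and last session". SAP Appendix 1 names the SP training checklist as its source, filled in straight after each simulated encounter. There the result is labelled "Change in mean competency % among intervention participants between the first and last session", so the SAP uses both interpersonal skills and competency for the same measure. Protocol section 3 agrees on who scores, since the secondary outcome is "measured by a score from SPs during the provider training intervention".

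The same actors have a teaching role. Protocol 6d states: "SPs will give verbal and written feedback on communication and counseling skills and will score HCWs using a standardized checklist". Section 7 gives the checklist both jobs; it is meant "to provide feedback for the HCW on their practice session and provide a score based on competencies met". Section 9a adds: "Data from the checklist will be shared with the HCW during the training session".

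The safeguards stated are a standardized checklist (6d) and actor training in SP methodology and the case scripts (6b). We found no rule on which actor or case is used at the first and last sessions, no scorer masked to session order, no rater calibration and no independent re-scoring. Videos are made for training (6d) and kept only where a waiver is signed (11b). The SAP will consider an SP random effect, but says so only for the primary between-arm model.

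**The concern.** A score produced as part of teaching is reused as a trial outcome. An actor who has given an HCW feedback on day 1 and scores the same HCW at the last session is partly judging the effect of her own advice. She can also tell that the course is ending. If she scores more generously then than a rater did at the first session, the difference enters the outcome as improvement.

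The primary comparison has a control arm rated by unannounced actors, which offers some protection against rater drift. This outcome has none: it is a within-person change in one arm, so a shift common to last sessions passes straight into the estimate. Making all scenarios equally difficult would not remove it. Nor would a random intercept for actor, because a generosity shared by all actors at last sessions is not a difference between actors.

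At stake is the interpretation of the SAP's only named secondary outcome: a reported gain in interpersonal skills could be partly or wholly a change in rating.

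**Working it through.** The documents give no sample size, power or test for this outcome, so there is no figure of theirs to reproduce. The check has two parts.

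**1. Does the text leave the path open?**
- Who scores: SP actors (Protocol 3, 6d, 7).
- Who gives feedback: SP actors (6d), on the same instrument (7).
- Is a comparison group scored on this checklist? No; the outcome is confined to the intervention arm (SAP Study Outcomes, Appendix 1).
- Is the last scorer required to be new to the HCW? No rule found.
- Is the last scorer stated to be someone who gave that HCW feedback? No. The text refers to SPs in the plural and to scenario-specific checklists, so different actors may already be used.
- Does sharing the score separate the two sessions? No. Section 9a shares checklist data without distinguishing sessions. Write observed change = (true last + leniency last) − (true first + leniency first). Leniency that arises because the HCW will see the score is in both terms and largely cancels. Only the growth, leniency last − leniency first, biases the change.

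**2. How much growth would matter? (illustration only)**

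Inputs:
- Item scale: seven items scored 0-3, 21 points in all, borrowed from the unannounced checklist (SAP, primary outcome). The training checklist's scale is not given in the text.
- HCWs: 10 per site (Protocol 5d) × 12 intervention sites = 120.
- ICC: 0.15, the value in the sample-size tables, applied here to the change score by assumption.
- SD of change: 15 points assumed, range 10 to 20.
- True change: zero.
- Test: two-sided 5% t test with 11 df (12 facilities − 1), critical value 2.20. The SAP does not specify this test.

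One category on one item = 100/21 = 4.76 points. Half of that, on average, = 2.38 points.

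Design effect = 1 + (10 − 1) × 0.15 = 2.35.

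SE of mean change = SD × √(2.35/120):
- SD 10: 1.40
- SD 15: 2.10
- SD 20: 2.80

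Chance of p<0.05 from drift alone (noncentral t, noncentrality = drift/SE):

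| Mean drift | SD 10 | SD 15 | SD 20 |
|---|---|---|---|
| 2.4 points | 34% | 18% | 12% |
| 4.8 points | 87% | 54% | 34% |

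For SD 15 the noncentralities are 2.38/2.10 = 1.13 and 4.76/2.10 = 2.27. The smallest drift that would itself be significant at SD 15 is 2.20 × 2.10 = 4.6 points, about one category on one item.

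A second route uses the SAP's baseline SD of 17.7 with an assumed first-last correlation ρ from 0 to 0.7. Then SE = 17.7 × √(2(1 − ρ)) × √(2.35/120), which is 3.50 at ρ = 0 and 1.92 at ρ = 0.7. With a normal critical value of 1.96, the smallest significant drift is 6.9 down to 3.8 points, the same order of size.

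**The case against.** The strongest reply is that the bias is supposed, not shown. No section says that the actor at the last session had earlier given that HCW feedback, and trained facilitators oversee the debriefings. That stands. A reader might infer from 6d that actors grade their own coaching and that the change is therefore pushed upward. The documents do not support that; they only fail to prevent it.

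A reader might also infer that sharing the score with the HCW inflates the change. It does not do so by itself, since the first score is shared as well. Withholding scores would also alter the feedback that forms part of the intervention.

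The illustration sets the size of the drift rather than estimating it. It borrows a scale from another instrument, and it uses a test the SAP does not plan: the SAP's model is for the primary comparison, and Table 6 has no row for the training change. All of this stands, so the percentages show sensitivity and do not predict results. At a quarter of a category (1.2 points, SD 15) the chance is about 8%, little above the nominal 5%.

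The SAP's timing in Appendix 1 makes scoring before that session's feedback the natural reading, though it is not a stated rule. Masking the scorer to session number would be weak in a 2-day course with groups of 5-10.

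What remains is that the outcome has no comparator and the plan does not separate the last scorer from earlier feedback to that HCW. The later SAP is explicit about this definition, even though Protocol 8b, with its similar GLMM, could suggest a between-arm comparison.

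**Conclusion.** The point holds as an open risk in how the secondary outcome is measured. The first-to-last change cannot separate skill gained from leniency that grows between sessions, and nothing in the plan limits the part that comes from an actor having already given that HCW feedback.

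Under the illustrative assumptions (borrowed 0-3 scale, 120 HCWs, ICC 0.15, SD of change 15, no true change), an average drift of half a category on one item would give a significant gain in about 18% of trials (12% to 34% over the SD range). A full category would do so in about 54% (34% to 87%). The real drift is unknown and could be nil.

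The primary outcome is not affected: it comes from a separate checklist at unannounced visits in both arms. That checklist also gives a between-arm communication score (SAP Table 6), so a controlled answer on communication is already planned. The change is worth making because it is cheap, not because the trial's main conclusion depends on it.

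**What to change.** In Protocol 6d and SAP Appendix 1:

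1. Use a counterbalanced rotation of the existing actors and cases. Each HCW's last scored session is rated by an actor who has not given that HCW feedback, and each actor scores similar numbers of first and last sessions. The balance matters because rotation alone could bring in differences in rater severity.
2. State that the checklist is completed before that session's feedback is given.

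In the SAP (Study Outcomes):

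3. State that this uncontrolled change is a descriptive training measure, and that the conclusion about communication skills rests on the between-arm communication score from the unannounced checklist (Table 6).

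The cost is wording in two documents, a rotation list and slightly harder scheduling in a small course; no staff are added. HCWs can go on seeing their numeric scores. Rotation removes the own-feedback part of the problem only. Practice effects and an actor's awareness that the course is ending remain, which is why the descriptive label is needed as well.
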